- To assess the efficacy of Lambda (180 mcg SC injections) vs. saline placebo injection in inducing PCR negativity at days 3, 7 and 14 among hospitalized subjects with symptomatic COVID-19 infection
- To assess the efficacy of Lambda (180 mcg SC injections) vs. saline placebo injection in inducing symptomatic improvement in subjects with COVID-19 infection, assessed by daily symptom questionnaire
- To assess the efficacy of Lambda (180 mcg SC injections) vs. saline placebo injection in improving clinical outcomes (death, ICU stay, intubation) in subjects hospitalized with COVID-19 infection
- To evaluate the safety and tolerability of Lambda (180 mcg SC injections) vs. saline placebo injection

III. Study Design

This is a prospective randomized trial to assess the antiviral efficacy of Lambda (180 mcg SC injection) vs. standard of care in up to 20 subjects hospitalized with COVID-19 infection.

Visit schedule

After referral by the care team and informed consent, and once the subject is confirmed as COVID-19 positive on clinical testing, patients will have initial clinical lab testing performed during baseline (visit 1). After confirmation of inclusion criteria, patients will be randomized 1:1 to receive the first dose of Lambda or saline placebo at the baseline visit (visit 1). Nasal swabs for PCR analysis will be collected for all subjects on Days 3, 7 and 14. An optional Day 5 nasal swab collection will occur only for subject who remain hospitalized on Day 5. On day 7, subjects in the treatment arm will receive a second Lambda injection and subjects in the control arm will receive a second saline placebo injection. On Day 14, subjects will undergo laboratory measurements to confirm CBC and LFT values are within safe parameters. Research blood will be collected and stored for future testing to measure levels of pro-inflammatory cytokines (e.g. IFN- γ , IL-6, IP-10, MCP-1, TNF- α). Measurements will be performed using excess blood collected for clinical purposes wherever possible. Subjects will complete a daily symptom questionnaire from screening through Day 14 ([Appendix 5](#)).

Administration of Treatment

Upto an initial 30 hospitalized patients will be enrolled (consented), with a goal of 20 subjects randomized 1:1 to receive either Lambda 180 mcg SC injections or saline placebo injections.

Administration of first dose Lambda/placebo in relation to initial COVID-19 symptom onset will be documented in all subjects.

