8. Current or planned participation in an investigational new drug (IND) trial from 30-days prior to randomization through Day 14 post treatment.
9. History of full COVID-19 vaccination
 - a. Full vaccination is defined as >2 weeks post final vaccination dose

V. Investigational Product

Randomization, Blinding and Treatment Codes

This is a randomized, single-blinded controlled study. Subjects will be randomized 1:1 to receive Lambda 180 mcg SC injections vs. saline placebo injections.

Description and Handling

Lambda Formulation

Lambda injection is a sterile, nonpyrogenic, ready to use solution (0.4 mg/mL) that is clear to opalescent, colorless to pale yellow, and is essentially free of particles. Lambda injection is provided in a 1-mL long Type I glass syringe with a 29-gauge, ½-inch, thin-walled needle. The syringes are prefilled with a solution of Lambda Injection, mannitol, L-histidine, polysorbate 80, hydrochloric acid, and water for injections; they are intended for a single use (180 mcg dose). The study drug will be donated by Eiger Biopharmaceuticals. Swab kits and RT-PCR testing will be supplied by a contract research organization, Viroclinics.

Lambda Packaging and Labeling

Storage of the study drug will be done in the Massachusetts General Hospital Clinical Trials Pharmacy (MGH CTP) (directed by [name], PharmD). Study drug will be packaged and labeled per the Massachusetts General Hospital Investigational Pharmacy standard procedure and will adhere to federal guidelines.

Lambda Storage and Handling

Prefilled syringes should be stored in a refrigerator at 2 - 8°C (36 - 46°F) and protected from long-term (>24 hours) exposure to light. Lambda Injections should not be frozen. Until administered to the subjects, syringes containing the study drug should be stored in a secure area, accessible only to authorized site personnel or vendor (in the case of home health visits). During transport to subject homes (via ambulance vehicle for home health visits only), drug should be stored in a cooler with an ice pack. To ensure the stability and proper identification, study drugs should not be stored in a container other than the container in which they were supplied.

Saline Placebo

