Assessment of Adverse Events and Serious Adverse Events

The investigator or qualified sub investigator is responsible for assessing AEs and SAEs for causality and severity, and for final review and confirmation of accuracy of event information

and assessments.

Assessment of Causality for Study Drugs and Procedures

Assessment of relatedness will be made by a physician investigator with respect to the stage of the trial that the subject is in (screening, on-treatment, post-treatment) and further with respect to whether the event was related to Lambda/placebo where applicable. The following will be used to assess the relationship of the adverse event to the use of Lambda/placebo:

1. Probably related

- Event or laboratory test abnormality, with reasonable time relationship to drug intake
- Unlikely to be attributed to disease or other drugs
- Response to withdrawal clinically reasonable
- Rechallenge not required

2. Possibly related

- Event or laboratory test abnormality, with reasonable time relationship to drug intake
- Could also be explained by disease or other drugs
- Information on drug withdrawal may be lacking or unclear

3. Unlikely related

- Event or laboratory test abnormality, with a time to drug intake that makes a relationship improbable (but not impossible)
- Disease or other drugs provide plausible explanations

4. Unrelated

- Event assessed as having no reasonable possibility of being related to study drug

5. Unclassified

- Event or laboratory test abnormality
- More data for proper assessment needed, or additional data under examination
- Report suggesting an adverse reaction
- Cannot be judged because information is insufficient or contradictory
- Data cannot be supplemented or verified

The relationship of an AE or SAE to study procedures (e.g., invasive procedures such as venipuncture or biopsy) should be assessed using the following considerations:

- **No:** Evidence exists that the adverse event has an etiology other than the study procedure
- **Yes:** The adverse event occurred as a result of protocol procedures, (e.g., venipuncture)

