Extra consideration will be made regarding fever as an adverse event. Fever is noted as a less common (<10%) potential side effect of Lambda, as well as a common expected symptom of COVID-19 infection. To best distinguish between fever associated with COVID-19 and Lambda treatment emergent or exacerbation of fever, study investigators will adjudicate suspected causality by reviewing time elapsed

between Lambda administration and onset/exacerbation of fever. We acknowledge that this distinction cannot be made with complete accuracy.

Assessment of Severity

The severity grading of AEs will be assessed as Grade 1, 2, 3, 4, or 5 according to the Common Terminology Criteria for Adverse Events (CTCAE) Version 4.03, which can be found at http://evs.nci.nih.gov/ftp1/CTCAE/CTCAE_4.03_2010-06-14_QuickReference_8.5x11.pdf.

For AEs associated with laboratory abnormalities, the event should be graded on the basis of the clinical severity in the context of the underlying conditions; this may or may not be in agreement with the grading of the laboratory abnormality.

The distinction between the seriousness and the severity of an adverse event should be noted. Severe is a measure of intensity; thus, a severe reaction is not necessarily a serious reaction. For example, a headache may be severe in intensity, but would not be classified as serious unless it met one of the criteria for serious events listed above.

Reporting of Adverse Events

The Principal Investigator ([name]) will be immediately notified of any adverse events. These will be documented in detail in the Adverse Events Tracking Log and submitted each year at the time of continuing review. Adverse events will be reported to the PHRC as described in the PHRC policy on Unanticipated Problems Involving Risks to Subjects or Others.

VIII. Statistical Considerations

Data Analysis

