All subjects will be included in the primary intention-to-treat analysis as well as the analyses of secondary outcomes and observed safety events. The primary analysis will compare the proportion of subjects who are PCR negative at post-treatment Day 7 between subjects receiving Lambda vs. standard of care using Fisher's exact test, and the difference between the treatment groups will be estimated using the difference in proportions. Subjects who die during follow up will be considered not to have achieved viral clearance, for the purposes of statistical analysis. Subjects who are lost to follow up will be removed from the analysis, since we consider loss to follow up as being unrelated to our outcome of interest. A key secondary analysis will compare the mean change in quantitative PCR from baseline to Day 7 in the treatment group and placebo group using a two-sample t-test. This analysis will likely have more power to detect a treatment effect compared to the PCR negative analysis since a continuous outcome will be used.

Additional secondary analyses will compare the proportion of subjects who are PCR negative at post-treatment Days 3, 5, and 14 and the mean magnitude of viral load reduction using the same approach at Day 7. In addition, the time to PCR negativity will be compared using a log-rank test, and the difference between the treatment groups will be estimated using a Cox proportional hazards model. To compare changes in symptom scores over time, a linear mixed model will be used to estimate the difference in the change with time between the two treatment groups at each of the post-baseline timepoints. For safety endpoints, the proportion of subjects who experience each type of event will be compared between the Lambda vs. standard of care groups at Day 14 using Fisher's exact test. Additional analysis

will compare proportions of hospitalized subjects who experience progression of disease as reflected by transfer to ICU or intubation, and the length of stay among hospitalized subjects will be compared using the log-rank test. Subjects who die will be analyzed as having a length of stay censored at one day past the last follow-up date. Hence, subjects who die will be considered as having a greater length of stay than subjects who remain alive for the duration of the study. Statistical analyses will be completed using SAS (SAS Institute 2011, Version 9.4, Cary, NC).

Sample size and power calculation:

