This is a pilot study to assess the ability of Lambda to increase the proportion of subjects with PCR negativity at Day 7 compared to standard of care (placebo group) as a primary endpoint. We anticipate that no subjects in the standard of care arm will be PCR negative at Day 7, and we anticipate that 50% of subjects in the Lambda arm will be PCR negative at Day 7.

The treatment will be considered for further study if the proportion of subjects who achieve PCR negativity will be 30% higher at Day 7 in the Lambda arm compared to the standard of care arm. This would correspond to 3/10 subjects in the Lambda arm if 0/10 subjects were PCR negative in the standard of care (placebo) arm. Assuming 50% of subjects will be PCR negative, we have a 94% chance of observing 3 or more subjects who are PCR negative at Day 7. This shows that our sample size of 10 subjects per group is sufficient to have a reasonable chance to support further study given the proposed treatment effect. Additionally, demonstration of a reduction in viral load relative to the placebo arm will be factored into decisions to pursue further trials.

IX. References

3. Loutfy MR et al. Interferon alfacon-1 plus corticosteroids in severe acute respiratory syndrome: A preliminary study. *JAMA* 2003 Dec 24/31; 290:3222-8.

Appendices

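### Adverse events are compared between arms only by event type, so no planned adverse-event comparison is likely to show harm spread over several types; per-subject summaries should be added beside it

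*Combined protocol and SAP*

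**What the plan says.** Section II, Secondary Objectives, includes: "To evaluate the safety and tolerability of Lambda (180 mcg SC injections) vs. saline placebo injection". Section VIII, Data Analysis, meets this objective with one sentence on safety endpoints: "the proportion of subjects who experience each type of event will be compared" between arms "at Day 14 using Fisher's exact test". It does not define a type of event, and it states no significance level or sidedness. The same section also compares ICU transfer or intubation, and length of stay, but as disease progression and hospital course.

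Section VII collects more than Section VIII uses. The investigator is "responsible for assessing AEs and SAEs for causality and severity"; "The severity grading of AEs will be assessed as Grade 1, 2, 3, 4, or 5" under CTCAE 4.03; and "Assessment of relatedness will be made by a physician investigator" in five categories. Seriousness is defined separately. Outside definitions and reporting, grade and relatedness have one stated use, the stopping rule for an individual subject in Section III.

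**The concern.** A drug can harm many subjects in different ways. If each event type is tested alone in two groups of 10, most types will have one or two events, and Fisher's test cannot separate the arms at those counts. The result would be a list of non-significant single-event comparisons, with no pre-specified statement of how many subjects in each arm had a serious or severe event, or did not receive the second injection because of an adverse event. A pooled summary chosen after the data are seen would be post hoc. This matters because the criteria for further study in Section VIII name only PCR negativity and viral load, so the safety summary is what a later team would read for harm.

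**Working it through.** **Inputs from the documents.** 10 per arm (Section VIII, sample size: "our sample size of 10 subjects per group is sufficient"); 1:1 allocation (Section V); Fisher's exact test by event type (Section VIII).

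**Assumptions.** Two-sided 5% level; the event rates below; independence of types within a subject unless stated. None of these is in the documents.

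**The plan's own figure.** The only computed figure concerns efficacy: the chance of 3 or more of 10 at a 50% rate. 1 − (1 + 10 + 45)/1024 = 968/1024 = 94.5%, which agrees with the stated 94%. No safety figure is given.

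**Step 1: what one event type needs.** For *a* Lambda events and no placebo events, the two-sided p-value is 2 × C(10,a)/C(20,a).

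| Lambda vs placebo | p |
|---|---|
| 1 vs 0 | 1.00 |
| 2 vs 0 | 0.47 |
| 3 vs 0 | 0.21 |
| 4 vs 0 | 2 × 210/4845 = 0.087 |
| 5 vs 0 | 2 × 252/15504 = 0.033 |
| 6 vs 0 | 2 × 210/38760 = 0.011 |

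With one placebo event, the threshold is 7 vs 1 (p = 0.020); 6 vs 1 gives 0.057.

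**Step 2: illustration.** Six Lambda subjects each have a different event and no placebo subject has any. Each of the six planned tests is 1 vs 0, p = 1.00. Counted per subject, it is 6/10 vs 0/10, p = 0.011. This case is chosen to show the mechanism, not as a forecast.

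**Step 3: expected behaviour with five types.** Let s be the exact power of one per-type test in the harm direction. The chance that at least one of five flags harm is 1 − (1 − s)^5. The per-subject rate of any event is 1 − (1 − p)^5.

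- 20% vs 5% per type: s = 1.99%, so 1 − (1 − 0.0199)^5 = 9.6%. Per-subject rates are 1 − 0.8^5 = 67% and 1 − 0.95^5 = 23%; power 32%.
- 15% vs 3% per type: 3.6% by type against 30% per subject.
- 20% vs 5% with a latent correlation of 0.3 between types (simulation): about 9% against 21%.

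**Step 4: where the advantage goes.** These are hospitalized COVID-19 patients, so both arms may have disease-driven events. Add an independent background rate b to both arms: per-subject rates become 1 − (1 − b) × 0.8^5 and 1 − (1 − b) × 0.95^5.

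| Background b | Power, per-subject measure (20% vs 5% per type) |
|---|---|
| 0% | 32% |
| 10% | 25% |
| 20% | 19% |
| 30% | 14% |
| 40% | 10% |

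At 40% the pooled measure does no better than the 9.6% from the by-type tests. If harm sits in a single type, the order reverses: at 50% vs 2% the by-type test has 54% power. With a 30% background the pooled rates are 1 − 0.7 × 0.5 = 65% and 1 − 0.7 × 0.98 = 31%, with 16% power.

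**Step 5: are the data there?** The visit lists in Section VI after randomization name only serious events and those related to protocol procedures. The Section III stopping rule, the Section VII causality and grading text and the adverse-event row in Appendix 2 presuppose wider recording. Section VII grades by CTCAE 4.03, while Appendix 3 points to a different scale. Any SAE is within every version of the recording scope. For the second injection, Section III asks that the reason for a subject's withdrawal, including an adverse event, be determined.

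**The case against.** The strongest reply is that this is a pilot of up to 20 subjects with safety as a secondary objective, and that a pooled test would usually miss harm too. That stands: 21% to 32% power under favourable assumptions is not a firm test. The gain is mainly a pre-specified per-subject summary.

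A reader might infer that spread harm cannot show at all, or that the safety objective cannot be answered. The documents do not support that. By-type power is low, not zero; by-arm proportions for every type would exist; and the ICU or intubation comparison would pick up some severe harm, though under the name of disease progression. An undefined type could even include SAE or related event, although the plan does not say so.

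A reader might also infer that any Grade 3 or higher event should become the main safety comparison, with the by-type table reduced to description. Step 4 argues against it: pooling is diluted by background disease and loses when harm is concentrated in one type.

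Nor can the fix be called free on the ground that all the data are already recorded, given the conflicts in Step 5. Relatedness carries a further problem. The trial is single-blind, and Section V leaves the order display unblinded for the provider, so relatedness ratings may be influenced by knowledge of the arm. Section VII itself accepts that drug fever and COVID-19 fever cannot be fully told apart.

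**Conclusion.** The point holds in limited form. Followed as written, Section VIII compares adverse events only by type. At 10 per arm and an assumed two-sided 5% level, one type needs at least 5/10 vs 0/10 to reach significance, so no planned adverse-event comparison is likely to show harm spread over several types. Tolerability has no analysis. The size of the gain from a per-subject measure rests on assumed rates and on how many COVID-19 events occur in both arms: it runs from about a threefold advantage in power (32% against 10%) to none. A worthwhile, inexpensive improvement to the plan; it does not alter the primary analysis or the decision rule.

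**What to change.** In Section VIII:

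1. Keep the by-type Fisher comparisons and define what counts as a type of event.
2. Add per-subject comparisons by arm, with counts and the difference in proportions, of (a) any SAE and (b) second injection not given because of an adverse event. Count events that start or worsen after the first injection.
3. Add (c) any Grade 3 or higher event and (d) any event rated possibly or probably related, once two conflicts are reconciled: the recording scope (Section VI visit lists against Sections III and VII and Appendix 2) and the grading scale (Section VII against Appendix 3). Label (d) descriptive because the trial is single-blind.
4. Do not demote the by-type comparison, and do not name Grade 3 or higher as the main test.

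The cost is a few sentences and four table rows, plus the two reconciliations, which rows (c) and (d) cannot do without. The sample size and treatment do not change. The downside is that an overall measure mixes events of different importance and is diluted by COVID-19 events in both arms, which is why it belongs beside the by-type comparison and not in its place.

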- a. Historic diagnosis by PCR test may be at any time prior to hospitalization but subject must have documentation of a positive SARS-CoV-2 RT-PCR test within 72 hours of randomization
4. Female subjects of childbearing potential who engage in heterosexual intercourse must agree to use protocol specified method(s) of contraception as described in [Appendix 4](#)
5. Subject must be able to comply with the dosing instructions for study drug administration and able to complete the study schedule of assessments

Exclusion Criteria

1. Current or prior history of any of the following:
 - a. Clinically-significant illness or any other major medical disorder that in the opinion of the investigator, may interfere with subject treatment, assessment or compliance with the protocol
 - b. Treatment with IFN or other immunomodulatory/immunosuppressive agent within 12 months before screening.
 - c. Respiratory compromise requiring ventilatory support other than nasal cannula (mask, bipap or intubation and mechanical ventilation).
 - d. History of treatment with any of the following medications within five half-lives or 30 days before administration of the study drug (whichever is longer): anti-IL-6, anti-IL6R antagonists, Janus kinase inhibitors, ustekinumab (anti-IL-12/23), or anti IL-23 agents (guselkumab).
2. Pregnant or Nursing Females (a negative pregnancy test (urine or serum) is required during screening [if historic negative result within 48 hours prior to consent is not available] for WOCBP)
3. Life threatening SAE during the screening period
4. Subjects having the following laboratory parameters at screening
 - a. Platelet count <90,000 cells/mm³
 - b. WBC count <3,000 cells/mm³
 - c. ANC <1,500 cells/mm³
 - d. Hb <11 g/dL for women and <12 g/dL for men
 - e. CrCl < 50 mL/min
 - f. Direct Bilirubin level $\geq 1.5 \times$ ULN
 - g. INR ≥ 1.5 (except in the setting of concomitant anticoagulant use)
 - h. CRP >200 mg/L
5. Females who may wish to become pregnant and/or plan to undergo egg harvesting during the course of the study and up to 30 days of the last dose of study drug. WOCBP must abstain from breastfeeding and be willing to use effective birth control during through the week 4 post treatment follow-up visit.
6. Clinically-relevant alcohol or drug abuse within 12 months of screening. Use of any prohibited concomitant medications as described in [Section V](#)
7. Known hypersensitivity to IFN

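### Progression counts only ICU transfer or intubation, so a subject who dies without either is scored as not having progressed, although the clinical objective names death

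*Combined protocol and SAP*

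**What the plan says.** Section II (Secondary Objectives) includes the aim of "improving clinical outcomes (death, ICU stay, intubation) in subjects hospitalized with COVID-19 infection". Three outcomes are listed, death among them.

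Section VIII (Data Analysis) addresses this with an additional analysis of the proportions of subjects with "progression of disease as reflected by transfer to ICU or intubation". It names neither a test nor a time point for that comparison.

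The same section sets the analysis population: "All subjects will be included in the primary intention-to-treat analysis as well as the analyses of secondary outcomes and observed safety events". The only stated removal is for loss to follow-up.

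It gives two rules for deaths:

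- Viral clearance: "Subjects who die during follow up will be considered not to have achieved viral clearance, for the purposes of statistical analysis".
- Length of stay: "Subjects who die will be analyzed as having a length of stay censored at one day past the last follow-up date". The stated consequence is that "subjects who die will be considered as having a greater length of stay than subjects who remain alive for the duration of the study".

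For safety, "the proportion of subjects who experience each type of event will be compared between the Lambda vs. standard of care groups at Day 14", by Fisher's exact test. Death is not named in that sentence, but Section VII (Serious Adverse Event) lists it among the criteria for a serious adverse event.

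**The concern.** Two of the three outcomes in the objective carry over into the progression analysis, and death does not. Death also competes with the counted events, because a subject who dies first can no longer be transferred to the ICU or intubated. If nothing is said about such subjects, the worst clinical course is recorded as an absence of progression.

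At stake is how the clinical comparison reads. An arm in which a subject dies outside the ICU without intubation shows a lower progression proportion than its clinical course warrants. The distortion can favor either arm, depending on where the death falls.

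**Working it through.** **Inputs.** 10 subjects per arm, 20 in total (Section VIII, Sample size and power calculation). 4% mortality for COVID-19 infection in general (Section I). The share of deaths that occur without ICU transfer or intubation is not in the documents, so it is varied from 0% to 100%.

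**Step 1. The plan's own figure.** The plan gives no figure for progression. Its one design probability is a 94% chance of at least 3 PCR-negative subjects among 10 at a true rate of 50%. The exact binomial gives 1 - (1 + 10 + 45)/1024 = 968/1024 = 0.945, which agrees. This figure concerns Day 7 PCR negativity only and does not depend on how progression is defined.

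**Step 2. How such a death is scored.**

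| Question | What the plan provides |
|---|---|
| Does the subject stay in the analysis? | Yes. All subjects enter the secondary analyses, and only those lost to follow-up are removed |
| Is death a progression event? | No. Only ICU transfer and intubation are |
| Does a death rule apply? | No. One rule covers viral clearance, the other length of stay |

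The subject therefore adds 1 to the denominator and 0 to the numerator.

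**Step 3. Size per death.** 1/10 = 10 percentage points in the arm concerned.

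**Step 4. How likely one such death is.** Let m be the mortality over follow-up and s the share of deaths without ICU transfer or intubation. Then P(at least one in 20) = 1 - (1 - m × s)^20. With m = 4% as an assumption:

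| s (assumed) | m × s | P(at least one) |
|---|---|---|
| 0% | 0 | 0% |
| 10% | 0.004 | 7.7% |
| 33% (one third) | 0.0133 | 24% |
| 100% | 0.04 | 56% |

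Expected deaths from any route are 20 × 0.04 = 0.8.

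**Step 5. What it can do to the comparison.** The counts below are assumed for illustration. Differences are Lambda minus placebo, and p-values are two-sided Fisher.

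| ICU transfer or intubation, Lambda vs placebo | Uncounted deaths | As written | With death counted |
|---|---|---|---|
| 1/10 vs 3/10 | 2 on Lambda | -20 points, p = 0.58 | 3/10 vs 3/10: 0 points, p = 1.00 |
| 0/10 vs 5/10 | 1 on Lambda | -50 points, p = 0.033 | 1/10 vs 5/10: -40 points, p = 0.14 |
| 0/10 vs 4/10 | 1 on placebo | -40 points, p = 0.087 | 0/10 vs 5/10: -50 points, p = 0.033 |

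The third row shows that the omission can also hide a difference in favor of Lambda.

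**The case against.** The best defense is that death is not lost from the trial. It is a serious adverse event, serious adverse events are recorded at each visit, and the safety analysis compares each event type by arm at Day 14. The objective lists three outcomes and does not define a composite, so separate reporting could answer it. This stands in part. A reader might infer that mortality is never compared and the objective goes unanswered, but the documents do not support that. What remains is that the safety sentence does not name death, and a separate safety count leaves the progression proportion as it was.

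A reader might also infer that progression is the one endpoint without a death rule. It is not: the quantitative PCR t-test and the symptom mixed model have none either. Nor does the plan say that such a subject counts as a success. The non-event scoring follows from the definition, the all-subjects rule and the absence of a rule for this endpoint.

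On likelihood, the 4% is a general figure, not a 14-day risk in this cohort. Hospitalization may raise the risk. The exclusions for support beyond nasal cannula, for CRP above 200 mg/L and for a life-threatening event during screening may lower it. Section I attributes the mortality to acute respiratory distress syndrome, a course on which ICU transfer or intubation before death is plausible. No figure in the documents sets a lower limit on the share of deaths without either, so the range has to start at zero.

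Finally, any single event on a binary endpoint moves an arm of 10 by 10 points. That is true. The 10 points describe the size of one misclassification and do not by themselves make this endpoint important.

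**Conclusion.** The mismatch between Section II and Section VIII is real and needs no estimate to establish it. Followed as written, the progression analysis treats a death without ICU transfer or intubation as no progression.

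Each such death shifts its arm by 10 percentage points. The 0% to 56% chance of at least one among 20 subjects rests on two assumptions: that the general 4% mortality applies here, and that the share of deaths without ICU transfer or intubation may lie anywhere from none to all.

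The impact is modest. Progression is an unpowered additional analysis in a 20-subject pilot. A reader might infer that the main conclusion of the trial is at risk, but the documents do not support this: the primary PCR analysis already counts death as failure, and the decision on further study rests on Day 7 PCR negativity and viral load.

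**What to change.** In Section VIII (Data Analysis), define progression as death from any cause, ICU transfer or intubation by Day 14. Compare it between arms with Fisher's exact test, and report each of the three components, including mortality, by arm. This also supplies the test and the time point that the progression sentence lacks.

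The cost is one sentence. Deaths are already captured as serious adverse events, and Day 14 is the existing end of study. ICU transfer and intubation have no row of their own in the Appendix 2 schedule, but the present analysis needs them in any case. The sample size and the 94% figure do not change. The one small drawback is that the composite mixes outcomes of different severity, which the listing of components addresses.
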